#### 6.3 Statistical Methods

#### 6.3.1 Baseline Data

Characteristics of subjects in all 3 groups of the study will be described with proportions for categorical variables and means and standard deviations for continuous variables.

#### 6.3.2 Efficacy Analysis

We will calculate proportions for the clinical outcomes (enrollment, use, and completion of the Quitline program) and evaluate the magnitude and statistical significance of differences between the 3 groups. Intention-to-treat analysis will be used so that subjects will be analyzed according to the group to which they were initially randomized. Secondary analyses will describe results for participants as-treated. Categorical variables will be compared between groups using chi-square tests. Multivariable logistic regression models (that potentially include confounding variables) will be used to compare quit rate between groups. These models will include indicator variables for each of the financial incentive groups; the no financial incentive group will be the reference. The treatment groups will differ significantly from usual care if its indicator variable differs significantly from zero (p-value < 0.05 as criterion for statistical significance in a likelihood ratio or Wald's test). A Wald's test of the hypothesis that the two indicator variables are equal will also be performed (hypothesis that the probability of a subject quitting is the same for both financial incentive groups). We will explore for potential confounding by referral bonuses in the models and adjust if necessary.

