#### **FIGURE 1: STUDY DIAGRAM**

### **1 BACKGROUND INFORMATION AND RATIONALE**

#### 1.1 Introduction

Cigarette smoking remains a leading preventable cause of death in the US with substantial morbidity, mortality, and financial costs each year. Nearly 20% of US adolescents smoke cigarettes or use other tobacco products like e-cigarettes, 80% of youth who initiate smoking transition to regular use by young adulthood, and more than 90% of adult smokers initiate tobacco use before age 18, making prevention and treatment of adolescent smoking a critical health priority. Further, e-cigarettes are now the most common tobacco product used by teenagers, and adolescent use of e-cigarettes is strongly associated with transition to cigarette use. Pediatricians see the majority of the US child and adolescent population, and adolescents view pediatricians as trusted sources for credible health information. Consequently, pediatricians are uniquely positioned to screen for tobacco use in their patients, initiate treatment, and connect adolescents to smoking cessation services.

While evidence-based smoking cessation programs for adolescent tobacco use are available, including the quitline, text messaging, mobile phone apps and web-based programs, they are underutilized by teenagers. Although most youth smokers want and attempt to quit, few seek assistance to do so. Consensus guidelines and the US Preventive Service Task force emphasize that clinician counseling can initiate behavior change in adolescent tobacco users and effectively educate them about available smoking cessation resources. A critical knowledge gap is how to best to translate screening into effective service receipt and quitting.

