## 3.2 Allocation to Treatment Groups and Blinding

Randomization to the 3 groups will be based on an automatically generated randomization sequence (block randomization stratified by cigarette or e-cigarette use), managed through the Way to Health (WTH) Platform.

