#### 9 STUDY ADMINISTRATION

### 9.1 Treatment Assignment Methods

#### 9.1.1 Randomization

Randomization to the 3 groups will be performed via a random number generator used by the Way to Health platform and employ block randomization. Block randomization with stratification by cigarette and/or e-cigarette use will be used over simple randomization to ensure an equal number of participants among groups, considering the relatively small sample size.

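### Section 6.3.2 does not carry the product-type randomisation stratum into the analysis: the planned tests are valid, and stratifying them is a cheap, optional improvement

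*Combined protocol and SAP*

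**What the plan says.** **Randomisation.** Section 3.2 describes "block randomization stratified by cigarette or e-cigarette use". Section 9.1.1 says "Block randomization with stratification by cigarette and/or e-cigarette use will be used over simple randomization" and gives the reason as "to ensure an equal number of participants among groups, considering the relatively small sample size". Block size is not given. The two sections differ in *or* against *and/or*, so the stratum of dual users, whom 3.4.1 admits, is not explicit.

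**Analysis.** For enrolment, use and completion, 6.3.2 states "Categorical variables will be compared between groups using chi-square tests" and does not mention the stratum. For quitting it states "Multivariable logistic regression models (that potentially include confounding variables) will be used to compare quit rate between groups". The only committed terms are these: "These models will include indicator variables for each of the financial incentive groups; the no financial incentive group will be the reference". It then adds "We will explore for potential confounding by referral bonuses in the models and adjust if necessary".

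**Referral bonus.** Sections 9.5 and 9.7 define it: $5 per potentially eligible person referred, at most five referrals, for subjects enrolled after AM13, paid whether or not the referred person enrols. Section 9.5 keeps the referral log apart from the main study database and restricts it to handling contact attempts.

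**Purpose.** Section 6.4 sets feasibility and effect-size estimation as the goals, with 20 per group and no power calculation.

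**The concern.** Blocking within product type forces the arms to be nearly balanced on product. If product also predicts engagement, an analysis that ignores it uses a variance that is too large. Its tests reject too rarely under the null, lose power, and give wider intervals than necessary. In the logistic quit model there is a further issue: the odds ratio with a prognostic stratum in the model is a different quantity from the one without it. Including covariates only potentially therefore leaves open which odds ratio the pilot will hand to the larger trial.

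The referral sentence raises a smaller and separate question. It allows a data-dependent choice of model for the secondary outcome, with neither the variable (eligibility, any referral, number or dollars) nor the criterion stated.

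**Working it through.** **The plan's own figures.** 3 x 20 = 60. Seventy enrolled for 60 evaluable (3.3.2) implies a loss of 1 - 60/70 = 14.3%. The documents give no rate, effect size, power or stratum split, so everything below rests on assumed inputs: two-sided 5% tests, no continuity correction, and control rates by stratum of .20/.20, .25/.40, .20/.50 and .10/.50. The corresponding stratum odds ratios are 1, 2, 4 and 9.

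**Step 1: why the crude test is conservative.** With equal balanced strata, the chi-square test uses a variance proportional to p(1-p) at the pooled rate p. The actual variance is proportional to the mean of p_s(1-p_s) over strata. The actual null size is P(|Z| > 1.96/sqrt(ratio)).

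- Stratum OR 2: ratio (.1875+.24)/2 / (.325 x .675) = .2138/.2194 = .974; size about 4.7%.
- Stratum OR 4: ratio (.16+.25)/2 / (.35 x .65) = .205/.2275 = .901; size about 3.9%.
- Stratum OR 9: ratio (.09+.25)/2 / (.30 x .70) = .17/.21 = .810; size about 2.9%.

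Size falls; it is not inflated.

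**Step 2: simulation, two arms of 20, strata 10+10, treatment OR 6.** There were 200,000 trials per setting, so the Monte Carlo error is at most sqrt(.25/200,000) = 0.1 point.

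| Stratum OR | Null size, Pearson / CMH | Power, Pearson / CMH | Change (points) |
|---|---|---|---|
| 1 | 4.9 / 4.9% | 75.3 / 73.9% | -1.4 |
| 2 | 5.0 / 4.8% | 73.8 / 74.6% | +0.8 |
| 4 | 4.1 / 4.9% | 67.0 / 71.9% | +4.9 |
| 9 | 3.3 / 5.0% | 53.0 / 66.2% | +13.2 |

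At treatment OR 3 the changes are -2.0, +1.1, +5.4 and +8.9 points. For the three-group test with ORs 6 and 3, power goes from 65.7, 66.6, 58.6 and 41.9% to 65.3, 67.4, 62.9 and 54.9%.

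**Step 3: unequal strata.** Section 1.1 says "e-cigarettes are now the most common tobacco product used by teenagers", so a rare cigarette stratum is plausible. At OR 6 and 5/15 per arm, Pearson and CMH power are 75.4/74.2, 74.2/74.5, 68.5/71.2 and 59.0/68.3%. At 3/17 they are 75.4/74.1, 74.6/74.3, 69.9/70.4 and 64.2/69.0%, which is about neutral up to stratum OR 4.

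**Step 4: risk difference.** With n_s per arm in each stratum, the Mantel-Haenszel weights are n_s/2. The stratified difference is then the sum of n_s d_s over the sum of n_s, which equals the crude difference. With permuted blocks of 3 or 6 (size assumed), the two differ by 0.2 to 1.1 points on average.

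Mean 95% half-widths (1.96 x mean SE, 10+10, OR 6), crude against stratified, are 26.9/26.9, 27.5/27.1, 27.9/26.5 and 28.6/25.2 points. Coverage is 92.9/92.8, 91.9/91.9, 95.0/93.9 and 96.0/93.4%. The narrower stratified Wald interval therefore falls short of 95%. An n-1 variance covers 93.1 to 94.3%.

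**Step 5: quit-rate odds ratio.** Take a product-specific OR of 3 and control quit rates of .05/.10. The treated rates are .136/.250, so the pooled rates are .193 against .075 and the OR without the stratum is (.193/.807)/(.075/.925) = 2.95. In the same way, .05/.17 gives 2.82 and .05/.32 gives 2.49.

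**Step 6: size of the quit model.** In the three-arm model (20 per arm, 10+10), the likelihood-ratio test of one arm indicator has the following null size without and with the stratum: about 8% either way at .05/.10, 8.6 against 9.0% at .05/.17, and 4.5 against 6.2 to 6.5% at .05/.32. Empty arms are also a risk. At quit rates of 5%/15%, an arm has no quits with probability .95^10 x .85^10 = .118, and at least one of three arms does with probability 1 - (1-.118)^3 = 31%.

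**Step 7: referral adjustment, no true arm effect.** The assumed model has a common cause of referring and quitting. If earning does not depend on arm, the adjusted OR is 1.00. If 33% against 53% earn by arm, it is 0.86, or 0.95 if half the subjects are eligible. At 25% quits the SE of the log OR is sqrt(2 x (1/5 + 1/15)) = .73, so ln(.858)/.73 = -0.21 SE. Reporting whichever of the two models is significant adds 0.4 to 1.0 points of type I error over always adjusting.

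**The case against.** The case for leaving the plan alone is strong, and most of it stands.

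- The chi-square test is valid. A reader might infer that ignoring the stratum inflates false positives or biases the effect; steps 1, 2 and 4 show neither.
- A reader might also infer that stratifying implies product type is prognostic. Section 9.1.1 gives equal group sizes as its reason, and no section supplies engagement or quit rates by product.
- Section 6.4 makes no power claim, and clear gains need a stratum OR of 4 or more.
- Narrower intervals are not pure gain, because simple stratified Wald intervals under-cover.
- Adding the stratum does not by itself restore nominal size in a sparse quit model.
- To say that the plan leaves the odds ratio without meaning would overstate it. Either odds ratio is legitimate, and ln(3/2.49) = 0.19 is about a quarter of the .73 SE, even at stratum OR 9.
- On referrals, it would be wrong to call the bonus undefined, because 9.5 and 9.7 define it. No section ties it to arm, and the statistician is blinded to individual allocation (9.1.2), which partly limits a result-driven choice.

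What survives is narrower. The stratum is already being collected, and using it risks at most about 2 points of power against a possible gain of up to 13. A pilot whose product is effect sizes should also state in advance which odds ratio it reports. Blinding does not supply the missing referral criterion.

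**Conclusion.** Section 6.3.2 does not analyse by the stratum used in randomisation. This is a missed improvement in a valid plan, of optional priority. The textual gap is certain, but the benefit is conditional. It is nil or slightly negative if product type is not prognostic, about 5 points of pairwise power at stratum OR 4 and about 13 at OR 9 with equal strata, and less if one product is rare. These figures rest on assumed rates, treatment odds ratios and stratum splits. The crude risk difference is essentially unaffected. For quitting, naming the stratum settles which odds ratio is reported, but needs a method suited to few events.

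The referral sentence is a minor matter confined to the secondary quit models. Bonuses earned arise after randomisation and so cannot confound the arm comparison. Modelling them from the referral log would also conflict with the use limit in 9.5. The documents do not support reading it as a material bias: the expected effect is about 0.2 SE or less, and it is nil unless earning depends on arm.

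**What to change.** In 6.3.2:

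- **(a)** Compare enrolment, use and completion with Cochran-Mantel-Haenszel tests (generalised form for three groups), stratified by the randomisation stratum as coded in the platform. Report stratified risk differences with 95% intervals from a named small-sample method, not simple stratified Wald intervals.
- **(b)** Make the stratum a fixed covariate in the quit-rate model, so that one odds ratio is prespecified. Use a sparse-data method such as penalised likelihood or an exact approach.
- **(c)** Delete the referral-bonus sentence. Alternatively, replace it with one prespecified sensitivity analysis by enrolment before or after AM13. That status is fixed at entry and does not need the referral log.
- **(d)** As a supporting clarification, align the stratum wording in 3.2 and 9.1.1 and state where dual users are placed.

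**Cost.** The change is to wording and a little more analysis work, with no change to procedures, data collection or sample size. If product type is not prognostic, pairwise power falls by about 1 to 2 points.

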### 2 STUDY OBJECTIVES

The purpose of the study is to determine if financial incentives for adolescent smokers compared to no financial incentive increases engagement in a smoking cessation program.

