#### 2.1 Primary Objective (or Aim)

The primary objective of this study is to compare, through a pilot, randomized controlled trial, an incentive for Quitline engagement, an incentive for smoking cessation, or no financial incentive intervention on adolescent smoker enrollment and depth of engagement in a smoking cessation program (Free Smoker Quitline, hereafter referred to as the Quitline).

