### **6** STATISTICAL CONSIDERATIONS

#### 6.1 Primary Endpoint

The main outcome of interest is adolescent cigarette or e-cigarette user completion of the smoking cessation program, defined as the proportion of smokers identified in the clinic that enroll, use, and complete the Quitline program compared across the 3 study arms.

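### Section 6.3.2 names the incentive-versus-none and incentive-versus-incentive contrasts only for quit rate; for the primary outcome, Quitline completion, it names no contrast, effect measure or interval

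*Combined protocol and SAP*

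**What the plan says.** Section 2 gives the purpose as a comparison with control. The study is to "determine if financial incentives for adolescent smokers compared to no financial incentive increases engagement in a smoking cessation program". Section 2.1 compares the three conditions on "adolescent smoker enrollment and depth of engagement in a smoking cessation program".

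Section 6.1 sets the primary endpoint: "The main outcome of interest is adolescent cigarette or e-cigarette user completion of the smoking cessation program". It is defined as the proportion who "enroll, use, and complete the Quitline program compared across the 3 study arms". Cotinine-confirmed abstinence is secondary (Sections 2.2 and 6.2).

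Section 6.3.2 then gives two strands of analysis:

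- For enrolment, use and completion it plans proportions and will "evaluate the magnitude and statistical significance of differences between the 3 groups". The method named is general: "Categorical variables will be compared between groups using chi-square tests".
- The regression strand is introduced for another outcome: "Multivariable logistic regression models (that potentially include confounding variables) will be used to compare quit rate between groups". The arm indicators, the no-incentive reference, the 0.05 criterion and the Wald test of equal indicators all belong to these models, and the equality hypothesis is written in terms of the probability of quitting.

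Sections 3.2 and 9.1.1 stratify the block randomisation by cigarette or e-cigarette use. Section 6.3.2 does not mention the stratum. Section 6.4 gives 20 per group (60 in total) without a formal calculation, and names feasibility and effect-size estimation as the goals.

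**The concern.** The contrasts that answer the Section 2 question are written down, but for the secondary outcome. The quit-rate models cannot stand in for an analysis of completion. Under Quitline Delivered Treatment in Section 7.1, completing the program requires counseling calls as well as self-reported abstinence, so it is a different outcome from cotinine-confirmed quitting. The arms may also order differently on the two outcomes: Table 1 pays $15 per counseling call in the Quitline arm and nothing per call in the cessation arm, but $25 against $100 for a confirmed quit.

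What is at stake is the estimate that the pilot is meant to hand on. Section 6.4 wants effect sizes for a larger study. That calls for a named contrast on the primary outcome, on a named scale and with an interval. If the comparison is one overall test, a significant result would not by itself show that either incentive did better than none.

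**Working it through.** **The plan's own figure.** 3 x 20 = 60 agrees with Section 6.4. No event rates, effect size or power are given, so nothing further can be reproduced. All completion rates below are assumptions, in the order Quitline incentive / cessation incentive / none.

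**Method.** With n = 20 per arm, every outcome of three independent binomial arms (21 x 21 x 21) was enumerated. The uncorrected Pearson statistic is the sum over arms of (x − n·p)² / [n·p(1 − p)], where p is the pooled proportion of the arms compared. It was referred to chi-square at 0.05, with 2 df for all three arms and 1 df for a pair.

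**Step 1: direction.** The statistic does not change when the arms are relabelled.

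| Assumed rates | Pattern | 3x2 test rejects |
|---|---|---|
| 50/20/20% | Quitline incentive helps | 0.567 |
| 20/20/50% | both incentives do worse than none | 0.567 |

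**Step 2: one worked table.** Take 9/1/5 completers out of 20 each.

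- All three arms: p = 15/60 = 0.25, expected 5 per arm, 20 x 0.25 x 0.75 = 3.75. Statistic = (16 + 16 + 0)/3.75 = 8.53, 2 df, p = 0.014.
- Quitline versus none: p = 14/40 = 0.35, expected 7, 20 x 0.35 x 0.65 = 4.55. Statistic = (4 + 4)/4.55 = 1.76, p = 0.18.
- Cessation versus none: p = 6/40 = 0.15, expected 3, 20 x 0.15 x 0.85 = 2.55. Statistic = (4 + 4)/2.55 = 3.14, p = 0.08.
- Quitline versus cessation: p = 10/40 = 0.25, expected 5. Statistic = 32/3.75 = 8.53, 1 df, p = 0.0035.

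The overall result here comes from the difference between the two incentives. At true rates of 45/5/25%, the 3x2 test rejects with probability 0.81. In 0.18 of trials it rejects while neither incentive-versus-none test does.

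**Step 3: do directed contrasts gain power?** Not in general.

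| Assumed rates | 3x2 test | Quitline v none, 0.05 | Quitline v none, Bonferroni for two tests |
|---|---|---|---|
| 30/30/10% | 0.323 | 0.357 | 0.242 |
| 40/40/10% | 0.615 | 0.623 | 0.492 |
| 40/10/10% | 0.681 | 0.623 | 0.492 |

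**Step 4: multiplicity.** With a common rate of 20% to 30% and no adjustment, the chance of at least one false positive is 0.09 to 0.10 over the two incentive-versus-none tests, and 0.12 to 0.13 over all three pairwise tests.

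**Step 5: precision.** The Wald half-width is 1.96 x sqrt[p1(1 − p1)/20 + p2(1 − p2)/20]. At 50% v 20% it is 1.96 x sqrt(0.0125 + 0.0080) = 0.28. At 20% v 20% it is 0.25, and at 50% v 50% it is 0.31.

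**The case against.** The strongest reply is that Section 6.3.2 never says that the test is a single overall one. It speaks of chi-square tests in the plural, and pairwise tests fit that wording. This stands: the 3x2 reading is an inference, and steps 1 and 2 apply only if it is right. On the pairwise reading the gap is that the contrasts are unnamed.

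Three stronger readings are tempting, and the documents do not support them.

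- A reader might infer that the plan cannot answer its own question. But Section 6.1 compares completion across three arms, an overall test fits that wording, and the reported arm proportions show direction.
- A reader might infer that no effect size is planned. Section 6.3.2 does plan proportions and the magnitude of differences for enrolment, use and completion. What it lacks is a named contrast, scale and interval.
- A reader might infer that directed contrasts cost no power. Step 3 shows otherwise: the overall test does better when only one incentive works, and also in the other two rows once two contrasts share the 0.05.

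It can also be said that p-values matter little in a pilot. That is fair, but it strengthens the case for stating the effect measure and interval. Nor do the documents show that anyone would choose contrasts after seeing the data. There are only three pairs, and no incentive is the evident control.

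**Conclusion.** The point holds as a gap in specification on the primary outcome. The plan's contrast structure is attached to quit rate, and no other section extends it to completion or enrolment. The unadjusted chi-square leaves the randomisation stratum unused. The gap itself rests on the text alone. The 0.567 figure and the 9/1/5 example rest on the single-3x2 reading, 20 evaluable participants per arm and assumed rates.

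Pre-specified contrasts would make the pilot's estimates clear, not precise: half-widths of about 25 to 31 percentage points remain at the rates tried. It is a cheap improvement and does not call the design into question.

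**What to change.** In Section 6.3.2:

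1. Apply the two-indicator model to completion and to enrolment, with no incentive as reference, the cigarette/e-cigarette randomisation stratum as covariate, and the test that the two indicators are equal.
2. Report the risk difference of each incentive arm versus none, and between the incentive arms, with 95% CIs. Name one route in advance: a stratified score-type interval, or a standardised risk difference (predicted probabilities under each arm, averaged over all participants). If cells are sparse, fit the model by penalised likelihood.
3. State that these contrasts are exploratory and meant for estimation, or give a multiplicity rule.
4. Keep the three-group chi-square as a supportive overall test.

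The cost is a few sentences and a little more programming. The downside is more than one contrast on the primary outcome, which item 3 addresses. Sample size, data collection and conduct do not change.

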#### 6.2 Secondary Endpoints

The secondary outcome is to confirm abstinence, via salivary cotinine concentration of <30 ng per milliliter at 10 weeks after study initiation.

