#### 6.4 Sample Size and Power

The goals of this pilot project are feasibility and estimation of effect size and, therefore, no formal sample size calculations are performed. We anticipate 20 participants per group (60 total) will provide sufficient data to determine effect sizes to power a future larger grant.

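### Section 6.3.2 lets either a likelihood ratio or a Wald test decide the quit comparison; at 20 per arm, Wald cannot reject against an arm with no quitters and the likelihood ratio test can exceed 5%

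*Combined protocol and SAP*

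**What the plan says.** Section 6.2 makes cotinine-confirmed abstinence at 10 weeks the secondary endpoint ("The secondary outcome is to confirm abstinence"). Section 6.3.2 assigns its analysis to logistic regression: "Multivariable logistic regression models (that potentially include confounding variables) will be used to compare quit rate between groups". The model has one indicator for each incentive arm, and "the no financial incentive group will be the reference". An incentive arm differs from the reference if its indicator meets this rule: "p-value < 0.05 as criterion for statistical significance in a likelihood ratio or Wald's test". The comparison of the two incentive arms is settled separately: "A Wald's test of the hypothesis that the two indicator variables are equal will also be performed".

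The section does not say which of the two permitted tests governs the comparisons with the reference, or what follows if they disagree. No section gives a rule for sparse or zero quit counts.

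Section 6.4 plans 20 participants per group with no formal sample size calculation, and says why: "The goals of this pilot project are feasibility and estimation of effect size".

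**The concern.** Likelihood ratio and Wald tests agree in large samples. They need not agree with 20 per arm and few events. If an arm has no quitters, the maximum-likelihood log odds ratio is infinite, its standard error diverges and the Wald statistic goes to zero. The likelihood ratio statistic stays finite and can be large.

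An empty arm is plausible here. A confirmed quit needs a report of no tobacco use for 30 days, a completed swab and cotinine below 30 ng/mL, and Table 1 pays the reference arm nothing for a confirmed quit.

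Two things are at stake. First, at low quit rates, whether the pilot reports an effect on quitting may depend on which permitted p-value is read. Second, the odds ratio, which could feed the effect size that section 6.4 wants for a later grant, may not be estimable.

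**Working it through.** **Inputs.** 20 per arm (section 6.4); p < 0.05, taken as two-sided (section 6.3.2); analysis as randomised (section 6.3.2). The plan has no power figure to reproduce. All quit rates below are assumptions.

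**Chance of an empty arm.** P(0 of 20 quit) = (1 − p)^20. This gives 0.95^20 = 36% at a 5% quit rate, 0.90^20 = 12% at 10% and 0.80^20 = 1% at 20%. For at least one empty arm of two at a common rate, 1 − (1 − 0.3585)² = 59% at 5% and 1 − (1 − 0.1216)² = 23% at 10%.

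**Example 1: 0/20 vs 6/20.** The pooled rate is 6/40 = 0.15.
- Null log-likelihood: 6 ln 0.15 + 34 ln 0.85 = −16.908.
- Alternative: 6 ln 0.30 + 14 ln 0.70 = −12.217 (the empty arm contributes 0).
- Likelihood ratio statistic: 2 × 4.691 = 9.38, p = 0.002.
- Wald: with 4/20 quitters in the third arm, the fitted coefficient is about 22.7 with standard error about 17,768, p = 0.999.
- Firth penalised likelihood ratio: p = 0.008.

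Against 0/20, the likelihood ratio test rejects from 3 quitters upward, Firth and Pearson from 4, and Wald never.

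**Example 2: 1/20 vs 6/20, no empty arm.**
- Log odds ratio: ln(6/14) − ln(1/19) = 2.097.
- Standard error: √(1 + 1/19 + 1/6 + 1/14) = 1.136.
- Wald: z = 1.846, p = 0.065.
- Likelihood ratio: statistic 4.72, p = 0.030.

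**True size, unadjusted.** All 21 × 21 outcomes were enumerated for two arms of 20. Without covariates, the three-arm model gives the same pairwise tests.

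| Common quit rate | Likelihood ratio | Wald |
|---|---|---|
| 5% | 5.4% | 0.0% |
| 10% | 8.5% | 0.15% |
| 20% | 5.5% | 2.3% |
| 30% | 5.3% | 4.1% |
| 50% | 4.3% | 3.9% |

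Maximum size over common rates of 0.1% to 50%: likelihood ratio 8.5% (at 9.4%; above 5% between about 4.8% and 38%), Wald 4.2%, Firth 5.0%, Pearson 5.3%. At 23 per arm (70 enrolled, section 3.3.2) the likelihood ratio maximum is 8.7% and the Wald maximum 5.4%.

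**Power and disagreement, unadjusted.**

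| Quit rates | Likelihood ratio | Wald | Firth | Pearson | Likelihood ratio and Wald verdicts differ |
|---|---|---|---|---|---|
| 5% vs 30% | 62% | 20% | 59% | 59% | 42% |
| 10% vs 40% | 62% | 46% | 61% | 62% | 17% |
| 20% vs 50% | 53% | 48% | 49% | 53% | 5% |
| 30% vs 60% | 46% | 45% | 45% | 46% | 2% |

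In the first row, tables with an arm at 0 or 20 of 20 account for 34.6 of the 41.9 points of disagreement.

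**With stratum adjustment.** The simulation used 20,000 three-arm trials per scenario, an assumed equal split between two strata, and a stratum odds ratio of 1 or 2. At 5% vs 30%, power is 62–64% for the likelihood ratio test, 20–22% for Wald and 59–60% for Firth. At a common rate of 10%, size is 8.8–8.9% for the likelihood ratio test, 4.1–4.2% for Firth and 0.1–0.2% for Wald. Adjustment does not remove the problem.

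**The case against.** The stakes are limited. This is a secondary outcome in a pilot aimed at estimation, no decision rule hangs on the p-value, and a risk difference can be computed whatever test is used. That is true and keeps the point from being critical. But the plan sets a significance criterion, so the criterion should give one answer.

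The impact depends on assumed rates, and 42% is the high end. Smaller effects give 13% disagreement at 5% vs 10%, 23% at 5% vs 15% and 13% at 10% vs 20%. This stands: the problem is material at low rates and small once the reference rate is 20% or more.

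Section 6.3.2 also names chi-square tests for categorical variables, and Pearson gives p = 0.008 for 0/20 vs 6/20. But the same section assigns the quit rate specifically to the logistic model, and the general sentence does not displace that.

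Section 2.2 words the quit comparison as among those who report abstinence. Read literally, the arms would be smaller and of random size, and these figures would not apply. The intention-to-treat rule in section 6.3.2 supports the 20 per arm used here, but the dependency is real.

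The stated size limits are unadjusted. With stratum adjustment, Wald reaches 4.7% at a 30% quit rate and the likelihood ratio test gives 4.9–5.8% at 50%. Section 9.1.1 describes "Block randomization with stratification by cigarette and/or e-cigarette use", which may mean more than the two strata simulated, and adjustment for referral bonuses was not simulated.

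Firth does not rescue the odds ratio: for 0/20 vs 6/20 it is 18.4 with a profile interval of 1.9 to 2468. That is a reason to make the risk difference the main estimate.

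**Conclusion.** The concern holds. The rule allows two tests that can give opposite verdicts on the same data. One of them over-rejects at low quit rates, with true size up to 8.5% at a nominal 5%. The other cannot detect any difference from an empty arm, and it is the only test named for the incentive-versus-incentive contrast.

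The size of the problem depends on quit rates that the documents do not give. It is large when the reference rate is about 5% to 10% and small from 20% upward. The figures assume 20 analysed per arm, two-sided tests and, unless stated otherwise, no covariates. The consequence is confined to the significance statements and odds ratios for quitting; the primary Quitline outcome is untouched. The plan should be changed, but this does not threaten the trial.

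**What to change.** In section 6.3.2, replace both the open choice of test and the Wald-only contrast with one governing method for all three pairwise contrasts: Firth penalised-likelihood logistic regression, with penalised likelihood ratio tests and profile-likelihood confidence intervals.

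Report each pairwise risk difference with a 95% Miettinen–Nurminen score interval as the main estimate, in line with section 6.4, and give no second p-value for the quit outcome. State the expected precision: a half-width of about 21 points at 0/20 vs 6/20 (interval 11.2 to 52.2 points), 26 at 4/20 vs 4/20 and 30 at 10/20 vs 10/20.

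If no covariates are kept, the Pearson chi-square test would serve nearly as well as the single test. Firth is preferred because section 6.3.2 plans for covariates.

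The change is to wording only, and section 9.2 leaves the software open. The downside is nominal power: 1 to 4 points below the likelihood ratio test in the four scenarios. The gap is larger for smaller effects at low rates (15% against 24% at 5% vs 15%; 9% against 22% at 2% vs 10%). At 5% vs 15% the rates lie where the likelihood ratio test's own size is inflated, so part of that gap is not real power.
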